**Figure 2. Participant Flow Diagram**

**Overview of Study Design.** Our primary aim is to analyze the efficacy of the 6-month REAL-T intervention in a large-scale two-arm RCT. To achieve this aim, N=210 YAs with T1D will be randomized evenly to two conditions: REAL-T or usual care control. The primary outcome is A1c, with key secondary outcomes pertaining to psychosocial well-being (depressive symptoms, diabetes distress, and DQoL). In addition, we will examine the effects of REAL-T after 3- and 6-month no-treatment follow-up periods. Furthermore, we will analyze mediating mechanisms of the intervention's effects on outcomes through structural equation modeling, and conduct exploratory analyses to evaluate the cost-effectiveness, cost impact, and change in QALYs associated with the REAL-T intervention relative to usual care. Quarterly data collection visits, performed over a 12-month period, will enable longitudinal modeling of changes in glycemic control, psychosocial well-being, and other primary and secondary endpoints. In addition, blinded CGM data collected at baseline, 6 months (immediately post-intervention), and 12 months (long-term follow-up) will facilitate a more robust analysis of the impact of the REAL-T intervention on glycemic control, through

an examination of changes in glycemic variability, percent time in range, percent time in hypoglycemia, and percent time in hyperglycemia. Figure 2 provides an overview of data collection throughout the study period.

**Participants.** Eligibility criteria, as outlined in Table 3, were chosen to ensure a medically stable pool of participants and maximize the potential of therapeutic benefit. In addition, the intervention is most appropriate for those with demonstrated diabetes care challenges and risk of developing complications, as evidenced by an elevated A1c level. Because of key differences in the pathophysiology and management of T1D and T2D, we have elected to restrict participation to YAs with T1D only.

To verify eligibility, we need to confirm A1C. Estimated A1C will be used for initial enrollment, and verified through A1C test results received from our laboratory. Estimated A1C will be identified through: (1) recent A1C from participant's medical records (directly from EMR or self-report); (2) GMI (estimated A1c) from participant's CGM software; or (3) participant self-reports that A1C has consistently been >7.5%.

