Healthcare utilization		Study-specific survey; medical record reviews	Incidence of diabetes-related outpatient medical visits, ED visits, urgent care visits, hospitalizations	Monthly				

**Data Management and Analysis.** The study's analytic plan is outlined in brief in this section; for further details, please refer to the "Statistical Design and Power" attachment in the PHS Human Subjects and Clinical Trials Information section. **Data Management:** Data will be uploaded and stored in a REDCap database management system. REDCap is a secure, web-based application designed to support data capture for research studies, providing an intuitive interface for validated data entry. It also includes audit trails for tracking data manipulation and export procedures; automated export procedures for seamless data downloads to common statistical packages; and procedures for importing data from external sources. The REDCap website is password-protected and restricted to authorized users (See Data and Safety Monitoring Plan). Research assistants will enter and reconcile all data, with further data quality checks performed by the biostatistician. Prior to conducting hypothesis tests, baseline participant characteristics will be described using frequency distributions, histograms, and summary statistics. Sparse data may be recoded to dichotomous or ordinal data.

**Power and Sample Size:** The study is powered for an intention-to-treat analysis of our primary outcome, change in A1c over the intervention period (including 3 and 6-month data). Other analyses are designated as secondary,

**Table 6. Power, given 210 participants, for testing intervention effects on A1c over 6 months (Aim 1), 9 and 12 months (Aim 2), and mediators/secondary outcomes (Aim 3).**

A1c 0-6 months (Aim 1)			A1c 0-9 or 0-12 months (Aim 2)			SEM/mediation analysis (Aim 3)		
% $\Delta$	Effect size	6-month attrition	% $\Delta$	Effect size	Annual attrition	Effect size (path a/path b)	6-month attrition	
0.81	0.55	>.99	0.81	0.55	>.99	.26/.36	.95	.95
0.59	0.40	.93	0.59	0.40	.97	.36/.26	.92	.92
0.50	0.34	.82	0.50	0.34	.89	.26/.26	.89	.88

to control the type 1 error rate in identifying statistically significant changes in the primary outcome. Power analyses were conducted using proc glmpower in SAS using a 2-sided alpha of 0.05. As described comprehensively in the "Statistical Design and Power" attachment, we calculated power for a range of

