**Aim 2: Assess the post-intervention durability (3- and 6-months post-intervention) of REAL-T’s effects on glycemic control and psychosocial well-being.** Data analysis will be similar to that outlined in Aim 1, using mixed effects regression models, and will examine changes from baseline to 9 and to 12 months (i.e., 3 and 6 months post-intervention). In addition, we will explore the pattern of changes in A1c and other outcomes across the 4 study subintervals, stratified by treatment group. We will fit linear trends to the subintervals and test if model fit is improved significantly compared to models using fewer linear subintervals. Although analyses can be completed incorporating data from all time points in one model, the potential for varying effects over time has led us to frame our primary endpoints in terms of changes over specific shorter periods; exploratory analyses will consider possible longer-term patterns of change.

**Aim 3: Examine mediating mechanisms of REAL-T’s observed effects through structural equation modeling.** In Aim 3, we propose to test mediation of: (a) intervention effects by self-care behaviors on A1c and psychosocial well-being (Aim 3, Hypothesis 1); (b) self-care behaviors as well as psychosocial well-being by self-efficacy (Hypothesis 2); and (c) self-care behaviors by habit strength (Hypothesis 3). These potential mechanisms will be assessed via structural equation models which include both direct and indirect effects of intervention. The indirect effects will be estimated as the multiplicative effect of direct paths between intervention and the mediator and between the mediator and the outcomes.

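### Is the Aim 2 power in Table 6 too high, given that it exceeds Aim 1's at the same sample size and effect sizes?

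*Combined protocol and SAP*

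**What the plan says.** The study randomizes 210 participants in equal numbers: "N=210 YAs with T1D will be randomized evenly to two conditions: REAL-T or usual care control". The Power and Sample Size paragraph states "Power analyses were conducted using proc glmpower in SAS using a 2-sided alpha of 0.05". It names A1c change over the intervention as the primary outcome, using both the month-3 and the month-6 measurements, and makes all other analyses secondary.

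Table 6, titled "Power, given 210 participants, for testing intervention effects on A1c over 6 months (Aim 1), 9 and 12 months (Aim 2", puts Aim 1 and Aim 2 side by side. Each row gives A1c difference, effect size and power, first for Aim 1 and then for Aim 2. The first row reads "0.81 0.55 >.99 0.81 0.55 >.99" and the second "0.59 0.40 .93 0.59 0.40 .97". The third has a difference of 0.50, effect size 0.34, and power .82 for Aim 1 and .89 for Aim 2. The Aim 2 column is headed "A1c 0-9 or 0-12 months (Aim 2" and holds one power figure per row.

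The Aim 2 section says the analysis "will examine changes from baseline to 9 and to 12 months", using models similar to Aim 1. It explains that "the potential for varying effects over time has led us to frame our primary endpoints in terms of changes over specific shorter periods" and leaves longer-term patterns to exploratory work.

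**The concern.** Difference and effect size match in every row, so the standard deviation is the same in both columns: 0.81/0.55 = 1.473, 0.59/0.40 = 1.475, 0.50/0.34 = 1.471. Sample size and alpha are also the same. Dropout by month 12 should be no lower than by month 6. A change from baseline to a single later visit should then be no more precise than the change to month 6, yet the stated power is higher.

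If the Aim 2 figures really belonged to a test that pools on-treatment with follow-up visits, they would not describe the durability contrasts. An effect present at months 3 and 6 and gone at months 9 and 12 still averages (1 + 1 + 0 + 0)/4 = 0.5 of its size. The trial could then report a null durability result while believing it had .89 power when it had .82 or less.

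**Working it through.** **Inputs.** From the documents: n = 105 per arm (210/2), two-sided alpha .05, SD = 0.81/0.55 = 1.473, A1c differences 0.81, 0.59 and 0.50. Assumed, because the supplied text does not give them: one common correlation ρ between all visits (compound symmetry), equal dropout in both columns (none in the main calculation), and an effect that builds linearly to month 6 and is then held.

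**Step 1: a plain two-group comparison is not what was computed.** With λ = n·d²/2 and no gain from baseline, 105 per arm gives about .98, .83 and .69 for effect sizes 0.55, 0.40 and 0.34. Neither column matches, so both use repeated measurements.

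**Step 2: the reasoning behind the doubt.** If both columns are one-degree-of-freedom tests (df 208), the stated powers imply these noncentralities:

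| Effect size | Aim 1 | Aim 2 | Information ratio |
|---|---|---|---|
| 0.34 | 2.889 (.82) | 3.201 (.89) | (3.201/2.889)² = 1.228 |
| 0.40 | 3.452 (.93) | 3.859 (.97) | (3.859/3.452)² = 1.250 |

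The arithmetic is right, but the ratio means something only if the two tests have the same degrees of freedom.

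**Step 3: let Aim 1 be a group-by-time test over months 0, 3 and 6.** This is an ordinary reading of a primary analysis that uses both the month-3 and month-6 data and was powered in a general linear model procedure. It has 2 degrees of freedom.

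- Aim 2, change from baseline to month 9 or to month 12: the between-arm variance in SD units is (2/n)·2(1−ρ), so λ = n·d²/[4(1−ρ)], tested with F(1, 208).
- Aim 1, effects 0, d/2, d at months 0, 3, 6: λ = (n/2)·Σ(effect − mean)²/(1−ρ). The sum is d²/4 + 0 + d²/4 = d²/2, so λ = n·d²/[4(1−ρ)], tested with F(2, 207).

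The two noncentralities are identical. Aim 1 has lower power only because it spends a second degree of freedom.

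**Step 4: numbers, with ρ = .708, so 4(1−ρ) = 1.168.**

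| Difference | d = difference/1.473 | λ = 105·d²/1.168 | Aim 1, 2 df | Stated | Aim 2, 1 df | Stated |
|---|---|---|---|---|---|---|
| 0.81 | 0.5500 | 27.19 | .998 | >.99 | .999 | >.99 |
| 0.59 | 0.4006 | 14.43 | .932 | .93 | .966 | .97 |
| 0.50 | 0.3395 | 10.36 | .824 | .82 | .893 | .89 |

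All six entries agree to two decimals. With the rounded effect sizes 0.40 and 0.34, the same ρ gives .931 and .825 for Aim 1 and .965 and .894 for Aim 2, all within about .005 of the table. The correlation is the same at every visit, so no rise at later visits is needed. The month-9 and month-12 contrasts have the same variance, so one figure serves both.

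**Step 5: dropout.** With equal dropout of 10% or 20%, fitting ρ to Aim 1's .82 moves it to about .73 or .76 and leaves Aim 2 at .89 and .96. If month-12 dropout exceeds month-6 dropout by 5 points, Aim 2 is .87-.88 and .95-.96. At 10 points more it is .85-.86 and .94-.95. These fall somewhat short of the stated figures but still exceed Aim 1's .82 and .93, so those values are not a ceiling.

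**Step 6: a second test also fits.** Keep Aim 1 at one degree of freedom and take a linear slope. Total change has relative variance 2(1−ρ) over three visits and 1.6(1−ρ) over five, a ratio of 2/1.6 = 1.25. Scaling Aim 1 by that ratio gives .895 and .970 for 0-12 months.

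**The case for a change.** The strongest case for the doubt is that, with the same degrees of freedom in both columns, Aim 2 needs 23-25% more information, and at least 18-19% after the most favourable rounding. A single-visit contrast cannot supply that under Aim 1's correlation. On that footing the column fits a pooled 0-12 test, a pooled 0-9 slope reaches only .86 and .95, and a pooled test does not isolate durability. The arithmetic of this is correct.

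The two-degree-of-freedom reading is also an assumption, and linear build-up is the profile that suits it best. If three quarters of the effect were present at month 3, the sum in Step 3 would be 0.542·d² instead of 0.5·d². Aim 1 would gain about 8% in noncentrality and the gap between the columns would narrow.

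What stands is that the reader cannot tell from the supplied text which test, correlation and dropout rates produced the column. That gap cannot be charged to the plan. The sentence describing the power calculation is cut off mid-phrase. Table 6 has lost attrition sub-headings: Aim 3 shows two power figures under a single attrition heading. The plan also refers to a separate power attachment that was not supplied. Finally, the objection to a 0-12 average or slope is aimed at an analysis that the Aim 2 section does not propose as its durability test.

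**Conclusion.** The concern does not hold. A ceiling of .82 and .93 for the month-9 and month-12 contrasts follows only if Aim 1 was powered with one degree of freedom, and nothing in the protocol says so. Under a standard alternative, with ρ of about .708, equal dropout and linear build-up to month 6, single-visit Aim 2 contrasts have .97 and .89 power, exactly as printed. Estimates of lost power, or of larger A1c differences needed, all start from the one-degree-of-freedom step and fall with it.

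This shows that the table can be consistent with the Aim 2 analysis. It does not prove which test was used. It would be reasonable to ask the sponsor for the Aim 2 power test, correlation and dropout rates, but that is missing detail and not an error. The Aim 2 section already names the baseline-to-9 and baseline-to-12 changes as its analysis. Aim 2 is secondary, the row at 0.81 (the change reported from the team's earlier trial) is above .99 in both columns, and neither Aim 1 nor the sample size is affected.

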**Measures and Data Collection.** A trained research assistant, blind to condition assignment, will administer the assessments outlined in Table 5. All self-report measures have been validated in this age group. All diabetes-related measures are appropriate for use in T1D. We will assess A1c with a CLIA-waived point-of-care device (DCA Vantage) which collects capillary blood using a standard finger-prick procedure. If traditional in-person testing for A1c is not feasible, we will offer one of the following sample collection methods: (1) an in-person appointment on campus or in the community using socially-distanced methods such as contactless transfer of supplies and demonstration of sample collection from a safe distance; (b) contactless drop off and pick up of supplies in the community, or (c) mailing participants provide participants with a mail-in A1c kit. We will collect CGM data using Abbot's Freestyle Libre Pro blinded CGM, which will be placed by the research team at the assessment session and worn by participants on their upper arm for 14 days. If the research team is unable to apply the CGM in-person through traditional means, we will offer one of the following application methods: (1) an in-person appointment on campus or in the community using socially-distanced methods such as contactless transfer of supplies and demonstration of self-application from a safe distance; (b) contactless drop off and pick up of supplies in the community, or (c) mailing participants the CGM application kit with instructions along with a prepaid postage box to be mailed back. After completing the CGM data collection period, participants will remove the device and mail it to the study site in a postage-paid envelope for data download by the research team. The Libre Pro CGM was chosen because it requires no calibration, manipulation, or restriction of activities on the part of the participant, and does not interfere with a patient's use of a personal CGM or closed loop CGM-pump system. As noted in Figure 2, we will conduct the full assessment battery at baseline, 6 months (immediately after the intervention), and 12 months (long-term follow-up), and a slightly abbreviated assessment battery at 3 months (midway through the intervention), and 9 months. The 3-month and 9-month assessments serve several critical functions. These assessments will be conducted in-person through the REDCap mobile app on the study's iPads, via surveys through REDCap's secured electronic system, or mailed out to the participants' homes for completion and mailed back in prepaid postage envelope. If participants prefer, they can also complete surveys over the phone with a trained research assistant. First, collecting data on key outcomes midway through the intervention will contribute to our understanding of how changes unfold over time, and in relation to each other, during the intervention, facilitating future refinements to intervention dose and timing. Second, the resulting information will permit longitudinal modeling of changes in A1c and other key variables at quarterly intervals over the full study period. Finally, quarterly assessments will provide additional contact with participants in the usual care condition, increasing retention. As the standard of care for diabetes dictates quarterly assessment of A1c, self-care (e.g., meter downloads), and psychosocial well-being (e.g., depression screening), this measurement strategy reflects typical clinical care. Monthly surveys sent through a secured electronic system will be conducted to gather healthcare utilization data, which will facilitate more accurate recall of healthcare utilization, to supplement data from medical chart reviews.

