
**Table 5. Demographic, Clinical, and Psychosocial Assessments**

General Construct	Variable	Instrument	Description	Time Point				
				0	3	6	9	12
Demographic/ background		Study-specific survey; medical record reviews	Age; gender; race/ethnicity; education; employment; country of origin; duration of diagnosis; treatment regimen; comorbidities	X				
Treatment satisfaction		Patient Satisfaction Survey	14 items; adapted from physical therapy satisfaction survey; $\alpha=0.99$ . 			X		
Glycemic control	A1c	Axis-Shield Afinion point-of-care assay	CLIA-waived; meets NGSP certification criteria; correlation with laboratory A1c measure=0.991. 	X	X	X	X	X
	% TIR, % hyper, % hypo	Abbot Freestyle Libre Pro CGM	14-day factory-calibrated blinded CGM; MARD of 11.4% compared to capillary blood glucose reference values 	X		X		X
Psycho-social well-being	Diabetes quality-of-life	Audit of Diabetes-Dependent Quality of Life (ADD-QoL)	19 items; $\alpha=0.85$ ; assesses impact of diabetes on social, physical, and emotional functioning. 	X		X		X
	Diabetes distress	Diabetes Distress Scale (DDS)	28 items; 7 subscales. Total scale $\alpha=0.91$ , subscale range $\alpha=0.76-.89$ ; $r=0.56$ correlation with CES-D 	X		X		X
	Health-related quality-of-life	MOS SF-12v2	12 items; evaluates global physical and mental well-being; subscale $\alpha$ in patients with diabetes=0.83-0.85; $r=0.40-0.43$ concurrent validity with self-reported physical/mental health 	X		X		X
Self-care behaviors	Medication adherence	• Medication adherence self-rating	• 3 items; quantitative self-rating of adherence over 30 days; 0.55 correlation with MEMS 	X	X	X	X	X
	SMBG	• 14-day meter data	• Number of BG checks completed over 14 days.	X	X	X	X	X
	Global self-management	Diabetes Self-Management Questionnaire (DSMQ)	16 items, 5 subscales; subscale $\alpha$ range=0.72-0.83; $r=-0.53$ correlation with A1c in adults with T1D 	X	X	X	X	X
Habit strength		Self-Report Behavioral Automaticity Index (SRBAI)	8 items, 4 for each target behavior (SMBG and taking insulin/medication); assesses habit strength; correlation to corresponding behaviors ranges from 0.42-0.86. 	X	X	X	X	X
Self-efficacy		Diabetes Empowerment Scale-Short Form (DES-SF)	8 items; $\alpha=0.84$ ; self-efficacy for performing diabetes self-management 	X	X	X	X	X

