Finally, power for analyses of mediators and secondary outcomes using structural equation modeling (SEM) is excellent for effect sizes of at least .26 for the direct effects of intervention on the mediator (path a) and of the

mediator on the outcome (path b), which are reasonable to anticipate given effect sizes derived from previous literature (see “Statistical Design and Power” for additional details).

**Aim 1: Evaluate the efficacy of REAL-T in improving glycemic control and psychosocial well-being.** Our primary analysis will evaluate efficacy for changes in A1c on an intention-to-treat basis, assessing between-group differences using mixed effects regression models. Nonparametric or other robust statistical methods will be used to evaluate the effect of deviations from normality including outliers and truncated data (e.g. eligibility criteria of >7.5% A1c) on results. An advantage to mixed effects regression models is that they incorporate all available data even when data are incomplete, providing robust effect estimates and high statistical power, as well as easy comparisons of the treatment groups. We will also conduct sensitivity analyses to evaluate whether outliers or missing data are driving the observed effects, and moderation analyses to examine whether baseline clinical or demographic characteristics (e.g., age, gender, ethnicity, SES, treatment regimen, duration of diagnosis) modify any observed effects of the intervention. **Secondary analyses:** We will evaluate the impact of the intervention on psychosocial well-being and CGM-derived measures of blood glucose control. Analysis of secondary outcomes will assess between-group differences in signed change scores on measures of % time in range (the proportion of all time measured by the CGM when blood glucose is between 70 and 180 mg/dl), % time in hypoglycemia (the proportion of time blood glucose is below 70 mg/dl), % time in hyperglycemia (the proportion of time blood glucose is above 180 mg/dl), depressive symptoms, DQoL, and diabetes distress.

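### Secondary outcomes are compared as change scores with no adjustment for their own baseline named; if run unadjusted, about 2% to 50% of precision is lost (assumed correlation and SD ratio), and the fix is free

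*Combined protocol and SAP*

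**What the plan says.** The secondary analyses paragraph of Aim 1 reads: "Analysis of secondary outcomes will assess between-group differences in signed change scores on measures of % time in range". The list continues with the other two CGM percentages, depressive symptoms, diabetes quality of life and diabetes distress. No covariate is named. In Aim 1, baseline characteristics enter the analysis only as possible effect modifiers.

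Mixed models are named twice. For A1c, Aim 1 speaks of "assessing between-group differences using mixed effects regression models". For durability, Aim 2 says: "Data analysis will be similar to that outlined in Aim 1, using mixed effects regression models". Neither sentence says how baseline enters the model.

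The baselines are collected. Overview of Study Design describes "blinded CGM data collected at baseline, 6 months (immediately post-intervention), and 12 months (long-term follow-up"). Measures and Data Collection puts the full battery at the same three visits. Table 5 marks the CGM measures, the ADD-QoL and the DDS at 0, 6 and 12 months. As supplied, Table 5 shows no depressive-symptom instrument, so that baseline cannot be checked there.

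Data Management and Analysis limits what can be concluded: the "analytic plan is outlined in brief in this section; for further details, please refer to the" Statistical Design and Power attachment, which was not supplied.

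**The concern.** A change score subtracts the whole baseline value, which fixes the slope of follow-up on baseline at 1. If the true slope is smaller, the subtraction adds baseline noise to the contrast, and a chance baseline difference between arms is over-corrected. The Randomization section names random block sizes but no stratification factor, so such differences are not limited by design.

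Validity is not at stake, because randomization keeps the raw change contrast unbiased. What is at stake is precision for outcomes that Overview of Study Design treats as key secondary ones. The trial is sized on A1c. The only power shown for secondary outcomes is for the mediation paths of Aim 3, so nothing in the text shows a margin to spare for these arm comparisons. Wider intervals make a real effect on time in range, quality of life or distress easier to miss.

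**Working it through.** **The plan's own figure.** There is none to reproduce. Table 6 gives power for A1c and for mediation paths, not for the change-score comparisons of Aim 1.

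**Inputs.** From the documents: 210 participants randomized evenly, so 105 per arm; two-sided alpha 0.05. Assumed: ρ, the baseline to follow-up correlation, 0.3 to 0.7; k, follow-up SD divided by baseline SD, 0.8 to 1.25; both equal across arms; no attrition.

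**Formulas.** Let s0 be the baseline SD. Per participant:

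- raw change: s0²(1 + k² − 2ρk)
- adjusted for baseline: s0²k²(1 − ρ²)
- the difference between the two: s0²(1 − kρ)², which is never negative
- precision lost by raw change: (1 − kρ)² / (1 + k² − 2ρk), which is (1 − ρ)/2 at k = 1
- SE inflation: 1/√(1 − loss) − 1
- adjusted sample of equal worth: 105 × (1 − loss) per arm

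**Two examples.** At ρ = 0.5, k = 1: variances 1.00 and 0.75, loss 25%. At ρ = 0.3, k = 0.8: variances 1.16 and 0.5824, loss 0.5776/1.16 = 49.8%.

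| k | ρ | Loss | SE larger by | Equal worth, n per arm | Detectable difference, raw / adjusted | Power of raw change at the adjusted detectable difference |
|---|---|---|---|---|---|---|
| 1 | 0.3 | 35% | 24% | 68 | 0.460 / 0.371 | 62% |
| 1 | 0.5 | 25% | 15% | 79 | 0.388 / 0.336 | 68% |
| 1 | 0.7 | 15% | 8% | 89 | 0.301 / 0.277 | 73% |
| 1.25 | 0.3 | 22% | 13% | 82 | 0.523 / 0.463 | 70% |
| 1.25 | 0.5 | 11% | 6% | 94 | 0.445 / 0.421 | 75% |
| 1.25 | 0.7 | 2% | 1% | 103 | 0.350 / 0.347 | 79% |
| 0.8 | 0.3 | 50% | 41% | 53 | 0.418 / 0.296 | 51% |
| 0.8 | 0.5 | 43% | 32% | 60 | 0.356 / 0.269 | 56% |
| 0.8 | 0.7 | 37% | 26% | 66 | 0.280 / 0.222 | 60% |

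Detectable differences are in baseline-SD units, for 80% power, from the noncentral t distribution.

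**Outside the grid.** At k = 1 the loss is 10% at ρ = 0.8 and 5% at ρ = 0.9. It is zero when kρ = 1, for example ρ = 0.8 with k = 1.25. At k = 0.7 and ρ = 0.3 it is 58%.

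**Simulation.** With 40,000 trials per cell, 105 per arm and bivariate normal data, the losses were 34%, 24% and 14% at k = 1, and 1.6% and 49.6% at the two extreme cells. The mean error of both estimators stayed within 0.0015. ANCOVA on the follow-up value and change regressed on arm plus baseline gave the same arm difference to rounding error.

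**Does naming a mixed model settle it?** No. Take complete data at 0, 6 and 12 months, compound symmetry, k = 1 and 105 per arm. At ρ = 0.3, 0.5 and 0.7 the variance of the 6-month contrast is:

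- separate baseline mean per arm: 0.02667, 0.01905, 0.01143, exactly that of raw change, (2/105) × 2(1 − ρ)
- common baseline mean: 0.01733, 0.01429, 0.00971, exactly that of the adjusted analysis, (2/105)(1 − ρ²)

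The ratios are 0.65, 0.75 and 0.85, at 12 months as well as at 6. The gain therefore depends on how baseline enters the model, which the text leaves open.

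**The case against.** The strongest reply is that this rests on silence in an outline. The section calls itself brief and sends the reader to an attachment, where a covariate list would naturally sit. The quoted sentence names a contrast, not an estimator; change regressed on arm plus baseline also fits it. This stands as a limit: the supplied text shows an open specification, not a proven unadjusted analysis, and every figure above applies only if the analysis is run unadjusted.

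The range also depends on the chosen grid. Neither ρ nor k is in the documents, 2% is not a floor, and 50% needs a low correlation together with a 20% fall in SD. Entry on A1c of at least 7.5% may narrow the baseline spread of time in range and hyperglycemia, which would favor k of 1 or more for those measures. That is a fair inference, and it makes the k = 0.8 rows less likely for them. It does not remove the loss: at k = 1.25 and ρ = 0.3 it is still 22%. It also says little about quality of life or distress.

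The detectable differences assume no attrition and roughly normal estimates. Time in hypoglycemia is a bounded percentage, so its power figures are the least secure. The percentage loss itself does not involve the sample size.

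Finally, the same silence about baseline applies to the mixed model for A1c. That is true, but it does not weaken the point for the secondary outcomes.

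**Conclusion.** The concern holds as a point of specification and efficiency, not of validity. The supplied text sets a change-score comparison and names no own-baseline adjustment, although the baselines of the CGM measures, ADD-QoL and DDS are collected. If the comparison is run unadjusted, the plainest summary is a loss of 15% to 35% of precision (equal SDs, ρ 0.3 to 0.7). Over the wider grid of k it is about 2% to 50%, with zero possible when kρ = 1. In large samples the adjusted contrast is never less precise. Confidence is medium, because ρ and k are assumptions and the attachment was not seen. The change should be made, but the primary A1c analysis and the sample size do not depend on it.

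**What to change.** In the secondary analyses of Aim 1, and for the 12-month comparisons of these outcomes in Aim 2, state that each arm difference is estimated with the outcome's own baseline value as a covariate. Equivalent forms are ANCOVA on the follow-up value and change regressed on arm plus baseline; a mixed model with a common baseline mean across arms also serves. Report that adjusted difference with its confidence interval, and keep unadjusted change scores as description. If the attachment already says this, repeat the sentence here.

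The cost is wording and one degree of freedom. A change score already needs every baseline value, so no visit, participant or measurement is added.

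### The Aim 1 secondary outcomes are assigned a change-score comparison with no model or missing-data method; read naturally, this is an unadjusted complete-pairs analysis, less precise than a mixed model and open to bias from baseline-dependent dropout

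*Combined protocol and SAP*

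**What the plan says.** The Aim 1 paragraph under Data Management and Analysis treats its outcomes in two ways. For A1c: "Our primary analysis will evaluate efficacy for changes in A1c on an intention-to-treat basis, assessing between-group differences using mixed effects regression models". It adds: "An advantage to mixed effects regression models is that they incorporate all available data even when data are incomplete". A missing-data check follows, still in the A1c text: "We will also conduct sensitivity analyses to evaluate whether outliers or missing data are driving the observed effects".

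Under Secondary analyses the text becomes: "Analysis of secondary outcomes will assess between-group differences in signed change scores", and it applies this to time in range, time in hypoglycemia and hyperglycemia, depressive symptoms, DQoL and diabetes distress. It gives no model, covariates, visit pair, analysis population or missing-data rule for these outcomes.

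Table 5 marks CGM, ADD-QoL and DDS at 0, 6 and 12 months only, whereas A1c is measured at all five visits. Aim 2, whose heading covers psychosocial well-being as well as glycemic control, says: "Data analysis will be similar to that outlined in Aim 1, using mixed effects regression models". The section describes itself as brief and refers to a Statistical Design and Power attachment, which is not among the supplied documents.

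**The concern.** A change score exists only if both visits were observed. With no month-3 value for CGM, ADD-QoL or DDS, each participant has at most one Aim 1 change score. Even a mixed model fitted to that single score is therefore a complete-pairs comparison, and nothing in the text adjusts it for baseline.

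Two things are at stake. The first is precision: an unadjusted change score ignores how strongly baseline predicts month 6. The second is bias: if, say, participants with worse baseline values leave usual care more often but do not leave REAL-T more often, the remaining usual-care group starts from a different level and its mean change shifts through regression to the mean, with no treatment effect at all. Unequal dropout is plausible when only one arm has regular therapist contact. The Overview of Study Design calls the psychosocial measures key secondary outcomes, so this is not a side analysis.

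**Working it through.** **Inputs from the documents.** 210 randomised evenly, so 105 per arm (Overview of Study Design); visits 0, 6 and 12 (Table 5); two-sided alpha 0.05 (Power and Sample Size). The plan gives no power figure for the change-score comparison, so there is no figure of its own to reproduce.

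**Assumptions, because the supplied text gives no missing rates or correlations.** Outcomes have unit SD at each visit. The correlation ρ between months 0 and 6 is 0.5-0.7; it is 0.1 higher for months 6-12 and 0.05 lower for months 0-12. For precision: 15% missing at month 6; half of those return at month 12; 15% of month-6 attenders miss month 12.

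**Step 1: bias.** Let month-6 dropout in usual care follow a logistic model in baseline (log-odds 1 per SD), let dropout in REAL-T be unrelated to baseline, and let the true effect be zero. Then:

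- Mean change among those seen in usual care = (ρ − 1) × mean baseline of those seen. In REAL-T it is 0.
- Size of bias = (1 − ρ) × |mean baseline of those seen|.
- Integrating the logistic model over a normal baseline gives means of −0.091, −0.173 and −0.253 SD at 10%, 20% and 30% missing.
- Smallest bias: 0.3 × 0.091 = 0.03 SD. Largest: 0.5 × 0.253 = 0.13 SD.
- With the same missing rate in REAL-T, the two-sided type 1 error is about 6-12% (normal approximation).
- With log-odds of 0.5 per SD, the bias is 0.015-0.07 SD.

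**Step 2: source of the bias.** Keep the same complete pairs but add baseline as a covariate. Given baseline, the expected month-6 value is ρ × baseline in both arms whether or not the participant stayed, so the arm coefficient is zero. Simulation of a similar scenario gave a bias of about 0.001 SD. The bias therefore comes from not adjusting for baseline; dropping incomplete cases alone does not produce it.

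**Step 3: precision of the month-6 contrast.** Pairs per arm: 105 × 0.85 = 89.25.

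- Change score: variance = 2 × 2(1 − ρ)/89.25.
- Baseline-adjusted pairs: variance = 2(1 − ρ²)/89.25, which is (1 + ρ)/2 times the change-score variance.
- Three-visit mixed model with equal baseline means: variance from the summed information over missing-data patterns.

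| ρ | Change score | Adjusted pairs | Mixed model | Mixed / change | Mixed / adjusted |
|---|---|---|---|---|---|
| 0.5 | 0.02241 | 0.01681 | 0.01649 | 0.74 | 0.98 |
| 0.6 | 0.01793 | 0.01434 | 0.01399 | 0.78 | 0.98 |
| 0.7 | 0.01345 | 0.01143 | 0.01106 | 0.82 | 0.97 |

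The mixed model cuts variance by 18-26% against change scores, but by only 2-3% beyond baseline adjustment.

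**Step 4: baseline CGM also lost.** If 15% of baseline CGM is missing as well, pairs per arm fall to 105 × 0.85 × 0.85 = 75.9. The mixed-to-change ratio becomes 0.65, 0.70 and 0.75 (cuts of 25-35%) and the mixed-to-adjusted ratio 0.86, 0.87 and 0.88 (cuts of 12-14%).

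**Step 5: the baseline constraint matters.** Under the Step 3 missing rates, if baseline means are left free by arm, the raw month-6 contrast has 0.95, 1.16 and 1.52 times the change-score variance at ρ = 0.5, 0.6 and 0.7. Taken instead as a difference in change, the unconstrained model gains only about 5%.

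**The case against.** The strongest reply is that the plan never says incomplete cases are dropped. It also words A1c as a change while fitting it by mixed model, so change wording does not by itself identify a complete-pairs method. The Aim 2 sentence suggests that mixed models were meant for the psychosocial outcomes too, and the attachment may settle the matter. All of this stands: both the exclusion and the month 0-6 pair are inferences. It does not close the gap, because the A1c model has two post-baseline visits in the Aim 1 window, whereas CGM, ADD-QoL and DDS have one.

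A reader might infer that losing incomplete cases is itself what biases the comparison. Step 2 shows otherwise for this dropout pattern: adjusted complete pairs are essentially unbiased. A reader might also infer that the mixed model was chosen for A1c because it keeps incomplete cases. The plan calls this one advantage and also cites robust estimates, power and ease of comparison.

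Randomization follows baseline testing, so baseline surveys should seldom be missing and loss is mainly at month 6. CGM is the exception: the sensor is worn for 14 days after the session and then mailed back. The planned missing-data sensitivity analysis sits in the A1c text, and its extension to secondary outcomes is not stated.

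**Conclusion.** The point holds as a gap in specification with a practical consequence. The wording permits, and most naturally describes, an unadjusted complete-pairs comparison. The documents do not support calling it a stated exclusion of incomplete participants or a definite analysis error.

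Under the assumed rates, that reading costs 18-26% in variance against a three-visit mixed model with equal baseline means, or 25-35% for CGM if 15% of baseline recordings are lost. The 0.03-0.13 SD bias needs dropout that depends on baseline differently by arm; if the dependence is the same in both arms, or absent, this bias does not arise. Most of the gain, and removal of this bias, comes from using baseline properly; retaining incomplete cases is a smaller benefit. Every size here rests on assumed missing rates and correlations. The change is worth making before outcome data are seen, so that the method cannot be chosen in the light of the missingness.

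**What to change.** Replace the change-score sentence in Aim 1 with a model statement. For each secondary outcome, fit the values at months 0, 6 and 12 in one mixed model with:

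- categorical visit, and arm-by-visit effects after baseline only;
- baseline means constrained equal across arms;
- unstructured covariance;
- everyone randomised with at least one value.

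Take the month-6 contrast for Aim 1 and the month-12 contrast for Aim 2. Keep the signed change-score comparison as a sensitivity analysis. State the baseline constraint explicitly, since Step 5 shows that precision can be lost without it. If the Statistical Design and Power attachment already specifies such a model, cite it and align the Aim 1 text.

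The cost is a few lines of plan text and slightly more analysis work, with no new data. The model assumes data are missing at random given the observed values, and the plan should say so.
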